7.2 Futility and Toxicity Monitoring

The secondary endpoint is the complete remission rate (CRR). Remission will be evaluated 6 months after daratumumab and hyaluronidase-fihj plus pomalidomide maintenance therapy (approximately 9 months post ASCT). Complete remission is defined as achieving a negative immunofixation of serum and urine, disappearance of any soft tissue plasmacytomas, and < 5% plasma cells in bone marrow. In patients for whom only measurable disease is by serum FLC level, normal FLC ratio of 0.26 to 1.65 in addition to CR criteria is required. The futility and toxicity will be monitored during the study.

We desire that the CRR is at least 10% and the dose-limiting toxicity rate is no higher than 33%. Toxicity is defined as treatment-related unmanageable toxicities, including grade 3 non-hematologic effects or grade 4 hematologic effects, that require delay or termination of the treatment during cycle one. Futility and toxicity will be monitored by the Bayesian stopping boundaries calculated on the basis of beta-binomial distributions using the method of Thall, Simon, and Estey (30). Independence is assumed between CR and toxicity. Patients will be monitored in cohorts of size (8).

We will enroll a minimum of 16 patients before stopping. The following stopping rules and boundaries were developed using the Multc Lean application (version

2.1) from the MDACC Biostatistics department. The stopping rules are as follows:

$$\Pr [\theta_E < 0.10 | \text{data}] > 0.90$$

$$\Pr [T_E > 0.33 | \text{data}] > 0.95$$

Enrollment will be stopped early if there is > 90% probability that the CRR is < 10% or there is > 95% probability that the toxicity rate is higher than 33%. The notation θ_E denotes the marginal remission rate, assuming that θ_E follows a prior distribution of beta (0.2, 1.8). T_E denotes the toxicity rate, assuming that T_E has a prior distribution of beta (0.66, 1.34). The corresponding stopping boundaries for futility monitoring are as follows: enrollment will be stopped early due to futility if (# of patients with remission) / (# patients evaluated) \leq 0/16-24, 1/32, 2/40-48, or 3/56.

Stopping boundaries corresponding to this probability criterion for toxicity will terminate the trial if (# of patients with toxicity) / (# patients evaluated) \geq 9/16, 13/24, 16/32, 19/40, 22/48, or 25/56.

We will suspend accrual while waiting to assess patient outcomes.

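### The 16-patient minimum also covers cycle-one toxicity; limiting it to futility and adding a toxicity boundary of 6 or more in 8 would be a cheap safeguard

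*Combined protocol and SAP*

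**What the plan says.** All of the monitoring rules are in Section 7.2 (Futility and Toxicity Monitoring).

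- Schedule: "Patients will be monitored in cohorts of size (8").
- Minimum: "We will enroll a minimum of 16 patients before stopping". The sentence is not confined to either rule.
- Toxicity criterion: enrolment stops early if "there is > 95% probability that the toxicity rate is higher than 33"%. The toxicity rate "has a prior distribution of beta (0.66, 1.34").
- Toxicity boundaries (stop at or above): "9/16, 13/24, 16/32, 19/40, 22/48, or 25/56". None is given at 8 patients.
- Futility boundaries (stop at or below): "0/16-24, 1/32, 2/40-48, or 3/56". The remission rate "follows a prior distribution of beta (0.2, 1.8").
- Timing: a toxicity counts if it is among those "that require delay or termination of the treatment during cycle one". Section 5.1 defines a cycle as 28 days. Remission is read after 6 months of maintenance.
- Accrual is paused while outcomes are awaited, but no decision is attached to the result in the first 8 patients.

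The operating-characteristics table that closes Section 7.2 covers true toxicity rates from 15% to 45%.

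**The concern.** A minimum before stopping makes sense for remission. The endpoint takes six months, and a run of early non-responders is common even with an acceptable drug. The same minimum is carried over to toxicity, which is known within one cycle. If the first cohort showed 6, 7 or 8 toxicities in 8 patients, the posterior threshold would already be passed, yet the rule would allow a second cohort to be enrolled. What is at stake is the exposure of up to 8 more patients, and sometimes further cohorts, if the combination after transplant proves much more toxic than expected.

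**Working it through.** **Inputs (Section 7.2).** Toxicity prior beta(0.66, 1.34); limit 0.33; threshold 0.95; cohorts of 8; maximum 56; toxicity boundaries 9, 13, 16, 19, 22, 25 at 16, 24, 32, 40, 48, 56 patients.

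**Step 1: reproduce the plan.** With x toxicities in n patients the posterior is beta(0.66 + x, 1.34 + n − x). The boundary is the smallest x for which Pr(rate > 0.33) exceeds 0.95. At n = 16, x = 8 gives 0.903 and x = 9 gives 0.963, so the boundary is 9. The other five toxicity boundaries reproduce in the same way. All futility boundaries also reproduce, using Pr(rate < 0.10) > 0.90 with the beta(0.2, 1.8) prior.

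Exact enumeration of both rules, with remission and toxicity independent as the plan assumes and no look at 8, reproduces all 15 rows of the table to rounding. For remission 30% and toxicity 45% it gives 0.597 and 39.0 patients, against the stated 0.60 and 39.0. A toxicity look at 8 would give 37.9 patients in that row, so the table was calculated without one.

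**Step 2: apply the same criterion at n = 8.**

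| Toxicities in 8 | Pr(rate > 0.33) | Above 0.95? |
|---|---|---|
| 5 | 0.936 | no |
| 6 | 0.986 | yes |
| 7 | 0.998 | yes |
| 8 | 0.9999 | yes |

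The plan's own prior and threshold therefore give a boundary of 6 or more in 8.

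**Step 3: effect of adding that boundary.** This uses the toxicity rule alone. At each look the distribution of toxicities so far is convolved with a binomial(8, p), and the mass at or above the boundary is removed as stopped. Mean number treated = Σ n × Pr(stop at n), over looks before 56, plus 56 × Pr(no stop before 56). Pr(stop early) counts looks before 56, which is the convention that reproduces the plan's table.

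| True toxicity | Pr(≥ 6 of 8) | Mean treated, plan | Mean treated, with look at 8 | Fewer treated |
|---|---|---|---|---|
| 33% | 0.019 | 53.20 | 52.76 | 0.44 |
| 40% | 0.050 | 46.52 | 45.70 | 0.82 |
| 45% | 0.089 | 39.06 | 37.94 | 1.12 |
| 50% | 0.145 | 31.22 | 29.72 | 1.50 |
| 60% | 0.315 | 20.54 | 17.86 | 2.67 |
| 70% | 0.552 | 16.82 | 12.37 | 4.45 |

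Pr(stop early) at acceptable rates rises as follows: from 0.094 to 0.101 at 33%, from 0.010 to 0.013 at 25%, and from 0.0017 to 0.0026 at 20%.

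**Step 4: does the look at 16 catch the same trials?** After exactly 6/8, the next 8 patients must add 3 toxicities to reach 9/16. The chance that they add fewer than 3 is 0.315 at a true rate of 40% and 0.145 at 50%. In those trials accrual continues past 16.

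**Step 5: is the minimum needed for futility?** With 0/8 remissions, Pr(rate < 0.10) is 0.947, above 0.90. A look at 8 would therefore stop for futility with probability 0.80^8 = 0.168 at a true remission rate of 20%. The minimum prevents this, which is a sound reason to keep it for futility.

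**The case against.** The strongest reply is that the minimum is part of the rule. It is stated openly, the first listed boundary is at 16, and the table was computed that way. A reader might infer that the plan breaks its own stopping criterion, or contains an arithmetic error. The documents do not support that. The sentence giving the criterion follows the minimum and is naturally read subject to it, so 6/8 satisfies only the posterior half of the rule.

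A second reply concerns size. A reader who saw only the figures for 60% or 70% toxicity might expect several patients to be spared. Those rates lie outside the 15% to 45% that the plan tabulates, and nothing in the documents predicts them. Section 7.2 says that early loss of patients to adverse events is not expected. This stands, and it limits the weight of the point.

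Third, a minimum also guards against an extreme early run, since the prior is worth only 0.66 + 1.34 = 2 patients. At a true rate of 33%, 44% of trials with 6 or more toxicities in the first 8 would not reach 9/16. So it would be wrong to say that a minimum can have no purpose for toxicity. The price of dropping it is nevertheless only 0.007 in false stopping at 33%.

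Finally, the accrual pause, the individual delay and discontinuation rules in Sections 3.1.5, 3.2, 5.6, 5.7 and 5.12, and the safety reporting in Section 8 mean that early toxicity would not go unnoticed. None of these is a trial-level stopping rule at 8 patients. Some pages were not available, so oversight provisions there could not be checked.

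**Conclusion.** The point holds as a cheap improvement to a consistent design. One minimum serves two endpoints with very different reading times. For toxicity, it means that evidence stronger than the plan accepts at 16 patients (0.986 or more, against 0.963) cannot stop enrolment at 8.

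Across the upper part of the plan's own range the average gain is about 0.4 to 1.1 patients. The real value is protection if toxicity is unexpectedly high: 1.5 fewer patients on average at 50%, 2.7 at 60% and about 4.5 at 70%. The present table has no row above 45%, so it does not show how the rule behaves there.

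These figures assume full cohorts of 8, cycle-one toxicity known for every patient before the next cohort opens, a constant toxicity rate, and no stopping for futility.

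**What to change.** In Section 7.2, state that the 16-patient minimum applies to the futility rule only. Put 6/8 at the head of the toxicity boundaries, as the value given by the existing prior and threshold, and leave the other boundaries unchanged. Re-run the operating-characteristics table with the added look, and include rows at 50% toxicity and above. If the sponsor prefers to keep the minimum for toxicity, the section should give the reason and show those extra rows.

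The cost is a few words and one re-run. Maximum sample size, cohort size and trial procedures stay as they are. The statistical price is the small rise in false stopping shown above, 0.7 percentage points at the 33% limit.

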5.0 Treatment Plan

5.1 Overall Design and Plan of Study

This will be a single arm, open label phase II, single center study of maintenance therapy with daratumumab/hyaluronidase-fihj and pomalidomide post salvage ASCT in patients with multiple myeloma.

The total number of patients to be treated in this study is 56 evaluable patients.

Patients should complete 2 cycles of therapy to be evaluable. For patients who receive fewer than 2 cycles due to progressive disease will be considered evaluable. Patient who received < 2 cycles due to AEs will be inevaluable for efficacy (response). All the other analysis will be conducted using intention to treat dataset.

Patients will have standard restaging studies prior to initiation of therapy. Standard post transplant therapy per institutional guidelines will be unaltered including prophylactic antibiotics, vaccinations and restaging.

Each cycle will be defined as a 28 day cycle. Drug holidays and break in therapy including those due to holidays, physician discretion and drug delivery are allowed as needed.

5.2 Daratumumab 1800 mg/hyaluronidase-fihj 30,000 units will be given SC weekly for weeks 1-8, followed by every 2 weeks for weeks 9-24, and then every month for weeks 25 until progression. On day 1 of each cycle, doses may be held if clinically indicated (i.e., active infections) for up to 4 weeks. If longer than 4 weeks, the PI will

evaluate and determine if the patient can continue on trial or must be taken off study. After day 1 of each cycle, subsequent doses may be held/skipped if clinically indicated (i.e., active infections) per PI or treating physician's discretion.

If daratumumab administration does not commence within the specified window (Appendix A), then the dose will be considered a missed dose. Administration may resume at the next planned dosing date. A missed dose will not be made up. Any adverse event deemed to be related to daratumumab that requires a dose hold of more than 28 days will result in permanent discontinuation of daratumumab. Subjects who miss ≥ 3 consecutive planned doses of daratumumab for reasons other than toxicity will be withdrawn from treatment, unless, upon consultation with the sponsor and review of safety and efficacy, continuation is agreed upon.

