The operating characteristics of these rules are shown in the table below.

	True Pr(Response)	True Pr (Tox)	Pr (Stop Early)	Average # treated
1	10%	15%	0.32	46.0
2	10%	33%	0.38	44.0
3	10%	40%	0.55	39.1
4	20%	25%	0.04	54.4
5	20%	33%	0.13	52.0
6	20%	40%	0.36	45.6
7	25%	20%	0.013	55.5
8	25%	33%	0.10	52.8
9	25%	40%	0.35	46.2
10	30%	20%	0.005	55.8
11	30%	33%	0.10	53.1
12	30%	45%	0.60	39.0
13	40%	20%	0.002	55.9
14	40%	33%	0.09	53.2
15	40%	45%	0.60	39.1

The dataset for efficacy will be based on evaluable patients while the dataset for safety includes all patients who receive the maintenance therapy and will be

evaluated as intention to treat (ITT). Based on the toxicity profile of daratumumab, we do not expect to have patients who receive fewer than 2 cycles due to AE's.

Patient who received < 2 cycles due to AEs will be inevaluable for efficacy (response). All the other analysis will be conducted using intention to treat dataset.

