The associations between/among safety data, prognostic factors, and the response will be assessed using student t-test/Wilcoxon rank test, ANOVA/Kruskal-Wallis test, chi-squared test/Fisher's exact test, or Logistic regression model as appropriate. Complete remission rate will be estimated along with a 95% credible interval.

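### No complete remission rate in all treated patients is planned beside the evaluable one, and the term for patients evaluated is undefined although both monitoring rules use it

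*Combined protocol and SAP*

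**What the plan says.** Section 5.1 sets a general condition, "Patients should complete 2 cycles of therapy to be evaluable", and then two special cases. Early progressors count: "For patients who receive fewer than 2 cycles due to progressive disease will be considered evaluable". Early adverse-event (AE) stops do not, and section 7.2 repeats this: "Patient who received < 2 cycles due to AEs will be inevaluable for efficacy (response". For the rest, "All the other analysis will be conducted using intention to treat dataset". Section 7.2 bases efficacy on evaluable patients and safety on everyone who receives maintenance. Section 5.1 sets the trial size as 56 evaluable patients.

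Section 7.2 gives a reason for not expecting the exclusion to matter: "Based on the toxicity profile of daratumumab, we do not expect to have patients who receive fewer than 2 cycles" because of AEs.

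Section 7.3 plans one estimate: "Complete remission rate will be estimated along with a 95% credible interval". Neither section 7 nor any other section plans a CRR in all treated patients, or a count of exclusions with reasons.

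The futility boundary in section 7.2 is a ratio, "of patients with remission) / (# patients evaluated", and the toxicity boundary uses the same denominator words. Section 1.1 makes CRR the primary objective. Section 7.1 makes PFS the primary endpoint, and section 7.2 calls CRR secondary.

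**The concern.** Response is the one outcome that loses patients because of what happened to them on treatment. A patient who stops in cycle one for toxicity is a toxicity event but is absent from the response estimate. If such patients reach CR less often than the others, the reported CRR describes a selected group, and nothing beside it shows by how much.

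The reason for expecting none is thin. It is argued from daratumumab alone, although pomalidomide is also given, and the plan's own toxicity event covers toxicities "that require delay or termination of the treatment during cycle one", with a tolerated rate of up to 33%. That limit is not a forecast, and it counts delays as well as terminations, but it shows that early termination is foreseen.

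Two gaps sit beside this. Stops before 2 cycles for other reasons, such as the withdrawal listed in section 5.12, fail the general condition in 5.1 but are not explicitly dealt with. And because two datasets sit behind one undefined denominator, the data could be known before anyone decides which patients count at a futility look.

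**Working it through.** **1. The plan's own figures.** Inputs from section 7.2: CRR prior Beta(0.2, 1.8), toxicity prior Beta(0.66, 1.34), looks every 8 patients from 16.
- Futility: stop if Pr[Beta(0.2 + r, 1.8 + n − r) < 0.10] > 0.90. The largest r that stops is 0, 0, 1, 2, 2, 3 at n = 16, 24, 32, 40, 48, 56, as printed.
- Toxicity: stop if Pr[Beta(0.66 + t, 1.34 + n − t) > 0.33] > 0.95. The smallest t that stops is 9, 13, 16, 19, 22, 25, as printed.
- All 15 operating-characteristic rows reproduce to rounding by exact enumeration over looks 16 to 48 (row 1: 0.315 and 46.0, against 0.32 and 46.0).

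The boundaries are correct. They use one n for both outcomes at each look, so they cannot show who counts when some patients are inevaluable for response.

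**2. Effect on the reported CRR.** The documents give no exclusion count beyond none expected, so k is assumed. Since section 5.1 sets 56 evaluable patients, the k excluded are taken as additional. Take 14 CRs among the 56 (25%, one of the response rates in the 7.2 table) and no CR among the excluded. All-treated CRR = 14/(56 + k), with intervals from the 7.2 prior:

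| k | CRR | 95% credible interval | Difference from evaluable |
|---|---|---|---|
| 0 (evaluable) | 14/56 = 25.0% | 14.4% to 36.2% | – |
| 2 | 14/58 = 24.1% | 13.9% to 35.1% | 0.9 points |
| 4 | 14/60 = 23.3% | 13.4% to 34.0% | 1.7 points |
| 8 | 14/64 = 21.9% | 12.5% to 32.1% | 3.1 points |

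The evaluable interval is 36.2 − 14.4 = 21.8 points wide.

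The sign depends on the excluded patients. With k = 4, one CR among them gives 15/60 = 25.0%, no difference. Two give 16/60 = 26.7%, so the evaluable figure would be too low. The latter is possible because sections 4.1 and 4.2 do not bar patients already in CR after transplant.

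**3. Can the denominator change a futility decision?** Take 40 treated patients and 2 CRs. The posterior probability that CRR is below 10% is:

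| Patients counted | Probability | Above 0.90? |
|---|---|---|
| 40 | 0.905 | yes, stop |
| 39 | 0.897 | no |
| 38 | 0.889 | no |
| 37 | 0.879 | no |
| 36 | 0.869 | no |

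So with 1 to 4 exclusions the rule stops on all treated patients and continues on evaluable ones. At 16, 24, 32 and 48 treated, 1 to 4 exclusions do not move the boundary.

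**4. What an all-treated futility denominator would do.** Let CRR be 10% among evaluable patients, with a fraction q excluded and none of them in CR. The all-treated CRR is then 0.10 × (1 − q). Futility-only stopping over looks 16 to 48:
- evaluable denominator: 0.315
- all treated, q = 5% (CRR 9.5%): 0.348
- all treated, q = 10% (CRR 9.0%): 0.383

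At 20% among evaluable patients the figures are 0.034, 0.043 and 0.054. The values of q are assumptions.

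**The case against.** The exclusion rule is prespecified and openly described, and the plan expects nobody to fall under it. CRR has no success threshold, PFS is analysed by intention to treat, and the trial is sized on PFS, which section 7.1 calls primary. The shift in step 2 is a fraction of the interval width and needs exclusions that the documents do not predict. All of this stands, and it limits the point to a reporting improvement.

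A reader might infer that the futility denominator is missing. It is not: section 7.2 writes one, and its dataset sentence, with the 56 evaluable patients in 5.1, points to the evaluable set. What remains is that the term is undefined and also serves the toxicity rule, whose dataset is all treated patients.

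A reader might also infer that futility ought to count all treated patients. The documents do not support that. It would replace the set to which section 7.2 points, and so change a decision rule. Step 4 shows the price: more futility stopping when CRR among evaluable patients is 10%, which meets the plan's stated minimum.

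Finally, the general condition in 5.1 could be read as excluding every early stop, including withdrawals. Only AE stops are expressly named as inevaluable, so the handling of the others is unclear rather than settled.

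**Conclusion.** The point holds as a cheap improvement. The text establishes the exclusion of early AE stops from response, the absence of an all-treated CRR, and the undefined denominator shared by two rules with different datasets.

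It does not establish that the CRR will be overstated, tempting as that reading is. That would need both exclusions and a lower remission rate among those excluded, and the documents give neither. Under the assumption of 2 to 8 exclusions with no CR among them, and 14 CRs in 56 evaluable patients, the gap is 0.9 to 3.1 percentage points. It vanishes at equal remission rates and reverses at higher ones. For futility, the ambiguity changes the decision only near a boundary, as at 40 treated with 2 CRs.

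How much weight CRR carries depends on reconciling section 1.1 with sections 7.1 and 7.2.

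**What to change.** In sections 7.2 and 7.3:
- Keep the evaluable CRR and report beside it the CRR, with its 95% credible interval, in all patients who receive at least one dose of maintenance.
- In that analysis, count a CR documented by the 6-month assessment and before any new anticancer treatment as CR, and everyone else as not in CR.
- Give the number excluded from the evaluable set, with reasons, and state how stops before 2 cycles for reasons other than AEs or progression are classified.
- Give the number counted as not in CR only because a result is missing, with a sensitivity analysis that leaves them out.
- Before the first look, define the patients-evaluated denominator separately for the futility and toxicity rules. The all-treated set need not be imposed on futility. If it were chosen, the stopping probabilities in step 4 should be weighed first.

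The cost is a few sentences, with no new procedure, accrual target or boundary. The all-treated CRR may read slightly lower than the evaluable one. Some true CRs off treatment may be counted as not in CR, because the off-treatment evaluations in Appendix A, footnote b, are partly at the clinician's discretion and list no marrow. The missing-result count and the sensitivity analysis show how far that matters.

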7.3 Analysis Plan

Patients' demographic, clinical characteristics, and safety data will be summarized using descriptive statistics such as mean, standard deviation, median, interquartile range, and frequency where appropriate.

Progression-free survival is defined as the interval from the date of initiation of maintenance therapy after salvage ASCT to the earlier of the first documentation of objective disease progression or death from any cause. Disease progression will be assessed using myeloma protein measurements in serum and 24 hour urine; serum free light chain assay; bone marrow biopsy examination with MGF-based MRD testing at 6 months (+/- 2 weeks) from the start of maintenance, and then yearly as indicated; skeletal survey or other imaging as clinically indicated; and, extramedullary plasmacytoma evaluation as clinically indicated. Progression is defined by the IMWG as a 25% increase from the lowest response value in any of the following: a) serum M protein with absolute increase ≥ 0.5 g/dL, b) urine M protein with absolute increase of at least 200 mg/24 hour, c) difference between involved and uninvolved FLC levels with absolute increase of at least 10 mg/dL (in patients without measurable serum or urine M protein), d) bone marrow plasma cell percentage with absolute percentage of at least 10% (in patients without measurable serum or urine M protein or FLC levels), e) new or definite increase in size of existing bone lesions or soft tissue plasmacytoma, f) development of hypercalcemia that can be attributed solely to myeloma. Data from surviving, non-progressing patients will be censored at the last time of follow-up. Progression-free survival will be summarized descriptively using the Kaplan-Meier method (including the median, 95% confidence interval, and survival curve). The proportion of patients alive and without disease progression at 6 months of daratumumab and hyaluronidase-fihj plus pomalidomide maintenance therapy will be summarized. The estimate will be accompanied by a two-sided exact 95% binomial confidence interval. In addition, a Cox regression analysis may be performed if demographic and clinical factors potentially affecting PFS are identified.

The associations between/among safety data, prognostic factors, and the response will be assessed using student t-test/Wilcoxon rank test, ANOVA/Kruskal-Wallis test, chi-squared test/Fisher's exact test, or Logistic regression model as appropriate. Complete remission rate will be estimated along with a 95% credible interval.

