5.12 Duration of Treatment and Patient Participation

Patients will be informed that they have the right to withdraw from the study at any time for any reason, without prejudice to their medical care. Patients will continue indefinitely unless the following occur:

- Lack of clinical benefit
- Patient's request to withdraw from the study or refusal of further therapy
- Unacceptable toxicity
- Pregnancy
- Physicians discretion
- Disease progression.
- Completion of up to 36 Cycles of study therapy

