6.0 Evaluation During Study

6.1 Treatment and Event Schedule (see [Appendix A](#).)

6.2 Efficacy measurements

Patients will be staged once every 3 cycles +/- 7 days while on protocol. Efficacy evaluations will be based on changes in: myeloma protein measurements in serum and 24 hour urine; serum free light chain assay; bone marrow biopsy examination with NGF-based MRD testing at 6 months from the start of maintenance (+/- 2 weeks); as clinically indicated skeletal survey or other imaging as clinically indicated; and, extramedullary plasmacytoma evaluation as clinically indicated.

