7.0 Statistical Considerations

7.1 Sample Size Justification

The primary endpoint of this study is progression-free survival (PFS). According to clinical trial [#NCT01998971 \(28\)](#), we expect that the median PFS without maintenance therapy is 12 months and the median PFS for the daratumumab-based maintenance therapy is expected to be 20 months. Given an accrual period of 36 months and a maximum follow-up time of 60 months, a sample size of 56 with the number of events of 42 will achieve the power of 0.91. The result is based on a two-sided test, a significance level of 0.05 with exponential assumption for survival time (29).

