Note: Study drug is defined as daratumumab and pomalidomide.																			
a) To occur within 7 days after discontinuation of all study treatment.																			
b) In the 90 (+3) days after the last dose of daratumumab for safety follow-up visits. For subjects who discontinue study treatment before PD, disease evaluations should continue to be performed at the frequency specified below until confirmed PD, death, start of a new anticancer treatment, withdrawal of consent to study participation, or end of the study, whichever occurs first. Once PD is confirmed, subsequent disease evaluation time points are not required.																			
- Every 8-12 weeks (± 3 days), at clinician's discretion: SPEP and 24-hour UPEP assessments, and serum calcium corrected for albumin																			
- Every 4 weeks (± 3 days), or at clinician's discretion: physical examination of extramedullary plasmacytomas if applicable																			
- Every 12 weeks (± 14 days), or at clinician's discretion: radiologic imaging of extramedullary plasmacytomas if applicable																			
- When CR is suspected or maintained: serum FLC, serum and urine immunofixation																			
- As clinically indicated: skeletal survey																			

- Evidence of clinical relapse will also be documented at the time at which it is first detected.

After PD is determined, patient will be taken off study and no further study evaluations will be needed.

- c) Blood pressure is to be measured at the following time points on Cycle 1 Days 1: immediately pre-administration, at the end of administration, 30 minutes post administration, 60 minutes post administration, and then hourly until 6 hours post administration. On Cycle 1 Day 8: immediately pre-administration, at the end of administration, 30 minutes post administration, 60 minutes post administration, and 120 minutes post administration. On Cycle 1 Day 15 onward: immediately pre-administration, at the end of administration, 15 minutes post administration. Infusion observation times and vital signs may be adjusted per PI discretion.
- d) Pre-infusion medications to be given before all daratumumab infusions (if necessary, oral pre-infusion medications may be administered at the subject's home on the day of the infusion, provided they are given within 3 hours prior to the infusion)
- e) Unless otherwise stated, all blood and urine samples must be obtained before administration of study treatment.

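### PFS is censored at an undefined last follow-up rather than at the last disease evaluation, so time without assessment could count as progression-free

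*Combined protocol and SAP*

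**What the plan says.** Section 7.3 runs PFS from the start of maintenance "to the earlier of the first documentation of objective disease progression or death from any cause". Its only censoring rule is "Data from surviving, non-progressing patients will be censored at the last time of follow-up". It does not define that date, mention the last disease evaluation, or say how new anti-myeloma therapy before progression is treated. PFS is then summarised descriptively by Kaplan-Meier.

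Appendix A, footnote b, covers patients who stop study treatment before progression: "disease evaluations should continue to be performed at the frequency specified below until confirmed PD, death, start of a new anticancer treatment". Withdrawal of consent and end of study also end evaluation. The off-treatment evaluations, "SPEP and 24-hour UPEP assessments, and serum calcium corrected for albumin", are due every 8 to 12 weeks. On treatment, Section 6.2 says "Patients will be staged once every 3 cycles +/- 7 days while on protocol". The Follow-up Phase of Appendix A also has a column headed Survival, every 12 weeks, which carries footnotes b and i. Once progression is found, footnote b says "After PD is determined, patient will be taken off study and no further study evaluations will be needed".

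Section 7.1 sizes the trial on PFS: "we expect that the median PFS without maintenance therapy is 12 months", against 20 months expected with the study regimen.

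**The concern.** A patient who starts new therapy without documented progression, and is alive, is literally a surviving, non-progressing patient. Disease evaluation has stopped for that patient. If the 12-weekly Survival contacts continue, the last follow-up is the last of those contacts, and every month since the switch enters the PFS analysis as progression-free although nobody looked for progression.

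Such patients are foreseeable. Section 5.12 lists lack of clinical benefit, toxicity, patient request and physician discretion as reasons to stop, separately from progression. Section 5.9 prohibits other systemic anti-myeloma therapy, so a switch means leaving study treatment.

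The error would favour the regimen, and a single-arm trial has no control group to share it. It matters whether PFS is labelled secondary (Section 1.2) or primary (Section 7.1), because the sample size rests on it.

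**Working it through.** **1. The plan's own figures reproduce.** Inputs from Section 7.1: N = 56, medians 12 and 20 months, 36 months of accrual, 60 months in all, two-sided 0.05, exponential times. Uniform accrual is assumed.

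- Hazard at a median of 20 months: λ = ln 2 / 20 = 0.03466.
- Expected events = 56 × [1 − (e^(−24λ) − e^(−60λ)) / (36λ)] = 56 × [1 − (0.4353 − 0.1250) / 1.2477] = 42.07 (stated: 42).
- Power = Φ(√42 × ln(20/12) − 1.96) = Φ(3.31 − 1.96) = 0.912 (stated: 0.91).

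The sizing arithmetic is therefore sound. The question is only what the censoring rule does to the data.

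**2. Who is affected.** Documented progression is an event and ends study evaluation. Patients who stop treatment without progression or new therapy are still evaluated, so last contact and last evaluation differ by at most about one interval. That leaves mainly patients who switch therapy without documented progression.

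**3. Size.** These inputs are assumptions, because the documents give none of them:

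- Patients leave assessment at r = 5, 10 or 15% per year, independently of progression risk.
- Survival after leaving is exponential with a median of 24 or 48 months. Deaths count as events, as Section 7.3 requires.
- Survivors are contacted to study end.

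Expected number leaving assessment = 56 × r/L × [1 − (e^(−24L) − e^(−60L)) / (36L)], with L = λ + r. At a true median of 12 months (λ = 0.05776) and r = 0.10/12 = 0.00833, L = 0.06610 and the result is 56 × 0.1261 × 0.9219 = 6.5 patients. At 5% and 15% it is 3.4 and 9.3.

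The sizing test uses z = [ln(ln 2 / 12) − ln(events / total time)] × √events and rejects upward if z > 1.96. Simulated results under the literal rule:

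| Leaving per year | KM median, true 20 (24-month / 48-month survival) | Upper-tail error, true 12 (24-month / 48-month survival) |
|---|---|---|
| 5% | 20.1 / 20.5 | 0.04 / 0.07 |
| 10% | 20.2 / 21.2 | 0.07 / 0.15 |
| 15% | 20.4 / 21.8 | 0.11 / 0.25 |
| Censored at loss of assessment, any rate | about 20.0 | about 0.02 |

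Simulation noise is about 0.01 in the error and 0.1 month in the median. The test reacts more than the Kaplan-Meier median because it uses total time at risk.

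**4. Price of the fix.** At a true median of 20 months and 10% per year, L = 0.03466 + 0.00833 = 0.04299. Expected events = 56 × (0.03466/0.04299) × [1 − (0.3564 − 0.0758) / 1.5477] = 37.0. Power = Φ(√37.0 × 0.5108 − 1.96) = 0.87, against 0.91 by the same formula with no loss. Direct simulation of the test gives 0.89 against 0.92.

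**The case against.** The strongest reply is that the premise is not in the text. No passage says that Survival contacts continue after new therapy. The column carries footnotes b and i, and both concern disease follow-up. The schedule as read shows no vital-status row, overall survival is not an objective, and patients leave the study at progression. The column may simply be the 12-weekly disease follow-up, in which case last follow-up and last evaluation nearly coincide. This stands, and it is why the point is conditional. It does not remove the need for a definition: two analysts could derive different PFS dates from the same records.

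A reader might infer that survival contact certainly continues and that PFS is therefore shown to be biased. The documents do not support that. A reader might also assume that every switcher stays alive to month 60. That would give error rates of about 0.13, 0.33 and 0.55, and Kaplan-Meier medians of about 21.1, 22.6 and 24.2 months. Those figures ignore deaths, which Section 7.3 counts as events, so they should not be used.

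The error rates belong to the exponential test, which appears only in Section 7.1. Section 7.3 plans a descriptive Kaplan-Meier summary and names no PFS test against 12 months. This also stands.

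Finally, last-evaluation censoring recovers 20.0 months here only because leaving assessment was simulated as independent of progression risk. If patients switch because disease is worsening short of progression, that censoring is also biased upward. This supports adding a sensitivity analysis; it does not support leaving the date undefined.

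**Conclusion.** The point holds conditionally. The rule is not tied to disease evaluation, and if contacts continue after new therapy it biases PFS upward. On the planned Kaplan-Meier summary the shift is modest: a true 20 months reads as about 20.1 to 21.8 under the assumed range. On the sizing test the upper-tail error would be about 0.04 to 0.25 instead of 0.02, which matters if a formal comparison with 12 months is made. Both ranges rest on assumed switching rates, assumed survival after switching, and independence of switching from progression risk. The stated sample size and power are unaffected. Severity is minor to moderate, and confidence is moderate because the documents leave open what the Survival contacts are.

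**What to change.** Replace the censoring sentence in Section 7.3 with:

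> Patients alive without documented progression are censored at the date of their last adequate disease evaluation. For patients who start new anti-myeloma therapy before progression, this is the last evaluation before that therapy.

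Define an adequate evaluation. Add one sensitivity analysis that counts new therapy before progression as a PFS event, because switching may be informative. State in Appendix A what the Survival contacts collect and whether they continue after new therapy.

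The cost is a few sentences and one extra analysis; no visit or procedure changes. PFS would rest on fewer events and slightly lower power: at 10% per year leaving assessment, about 37 events instead of 42 and power of about 0.87 to 0.89 instead of 0.91.
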